Long-term outcomes of successful chronic total occlusion percutaneous coronary interventions using the antegrade and retrograde dissection and re-entry approach.

(LOTUS-ADR/RDR)

Protocol

Sponsored by: Department of Cardiology, Xi'jing Hospital.

The Fourth Military Medical University (FMMU)

Approved by: Ethics Committee, Xi'jing Hospital. FMMU

Approved Ethical Number: KY20172019-1

Approved date: 2017.03.15

Last Update: 2018.11.20

Study Time: 2018.12.01- 2019.12.30

Versions: V2.0

ABSTRACT

BACKGROUND: Chronic total occlusion (CTO) angioplasty is one of the most challenging procedures remaining for the interventional operator. Today, with contemporary CTO negotiation available strategies and significant operator expertise, the literature reports a 50-95% success rate for recanalizing CTOs. But PCIs of CTO lesions still carry a high rate of in-stent restenosis (ISR). Because previous reports have not specifically compare contemporary antegrade and retrograde dissection and re-entry dissection (ADR/RDR) technique on the long-term impact of ISR, so the investigators focused on the objective.

OBJECTIVES: This study hope to evaluate the frequency of angiographic ISR and further elucidate some ISR related higher risk factors among CTO PCI patients in intimal stent group using antegrade or retrograde wire escalation (AWE/RWE) techniques and sub-intimal stent group using contemporary antegrade or retrograde dissection and re-entry (ADR and/or RDR).

METHODS: A total of 300 consecutive selected patients with CTO lesion who will undergo successful revascularization by AWE/RWE and ADR/RDR techniques treatment will be enrolled in this prospective multicenter registry from December 1 2018 to December 31 2019. The primary study endpoint of the protocol is the binary in-stent restenosis of CTO vessels at angiographic follow-up about 13 months. The secondary endpoints are: 1) CTO technique and procedure success rate; and 2) in-hospital and 30 days MACE (Cardiac death, acute myocardial infarction, urgent repeat target vessel revascularization with either pericardiocentesis or surgery and stroke and stent thrombosis and stroke); 6months and 1-year and 2-year MACE including death, MI, and target CTO vessel revascularization and stroke ; and 3) Restenosis scores (R-scores) of related risk factors.

CONCLUSIONS: This study expect to identify long-term effect of ADR and RDR methods on the ISR incidence and predictors.

INTRODUCTION

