④ Clinical success will be defined as a procedural success without In-hospital MACCEs. In-hospital MACCEs is defined as the composite of non-Q-wave and Q-wave myocardial infarction (MI), recurrent angina requiring urgent repeat revascularization with PCI or coronary bypass surgery, stroke, and death. Non-Q-wave MI is defined as creatine kinase-MB enzyme elevation >3 times the upper limit of normal. When new pathological Q waves, in addition to enzyme elevation, will be observed on the electrocardiogram, the event is defined as a Q-wave MI. In all patients, creatine kinase and creatine kinase-MB is evaluated 6 h after the procedure and until their normalization if levels is abnormal.

⑤ Lesion complexity will be judged using the J-CTO (Multicenter CTO Registry in Japan) score (0 ¼ easy, 1 ¼ intermediate, 2 ¼ difficult, 3 ¼ very difficult) (20) and calculated by allocating 1 point each for: non-tapered proximal cap (ie, blunt or ambiguous), any calcification, any tortuosity, occlusion length >20 mm and any prior unsuccessful attempt. J-CTO score of ≥ 2 was defined as complex.

⑥ CTO proximal cap location is defined according to American Heart Association (AHA) classification and additionally coded as either ostial or non-ostial and proximal (left main, proximal left anterior descending, proximal circumflex or proximal right coronary artery) or distal (all other sites). Cap morphology is coded as blunt or tapered, or as ambiguous when there is lack of clarity over the origin of the ongoing vessel. Calcification within the CTO is coded as none visible, mild (spots only), moderate (<50% of vessel circumference) or severe (>50% of vessel circumference). Tortuosity is assessed at baseline or after subsequent equipment passage and coded as straight (no bend or <45° single bend), slight (>45° single bend), moderate (2 bends >45° or 1 bend >90°) or severe (2 bends >90° or 1 bend >120°).

Disease proximal and distal to the CTO is classified as absent, mild, moderate or severe. Proximal or distal cap side branch is considered present if occurring ≤ 3 mm from the respective CTO cap. Occlusion length is estimated by dual injection, or from apparent length after guidewire crossing. Collaterals are classified according to Cohen and Rentrop and deemed interventional if, on angiographic inspection, are thought amenable to crossing by a guidewire and a microcatheter by the operator.

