and/or calcification) and presence of side branches of the target coronary vessel at the distal cap; and (d) size and suitability of collateral circulation for the retrograde technique. Several guidewire strategies are used, including the single-wire technique, the parallel-wires technique, the intravascular ultrasound–guided wiring technique, and retrograde wiring through collateral vessels, such as simple retrograde wiring, kissing wires, the knuckle technique, and the CART and reverse CART techniques, as previously described.

⑥ The number and type of approaches (AWE/ADR/RDR/RWE) required to cross the CTO segment are recorded. Wire crossing time is from insertion of the guidewire into either the target vessel or retrograde donor vessel to when the wire successfully crossed the CTO segment and re-entered the true lumen.

⑦ The occluded segment is stented with second generation DESs(XIENCE, Abbott) (if no contraindication for prolonged dual antiplatelet therapy) and post-dilation performed to optimize stent expansion and apposition as needed.

⑧ In this study, by evaluating CTO lesions in the pre-stenting and post-PCI period, the investigators seek to identify the predictors of ISR. The standard restenosis scores (R-scores) related six factors including: A: the number of stent ($n < 2$ 0score; $2 > n < 4$ 1score; $n > 4$ 2score); B: stent length ($< 35\text{mm}$ 0score; $36\text{-}70\text{mm}$ 1score; $> 71\text{mm}$ 2 score); C: lumen dissection length ($< 20\text{mm}$ 0score; $21\text{-}30\text{mm}$ 1score; $> 31\text{mm}$ 2score) ; D: calcification (mild 1score; severe 2score; E: lumen area ($< 5\text{mm}^2$ 3score; $5\text{-}7\text{mm}^2$ 2score; $> 7\text{mm}^2$ 1score) and F: angulation slight ($> 45^\circ$ single bend 1score), moderate (2 bends $> 45^\circ$ or 1 bend $> 90^\circ$ 2 score) or severe (2bends $> 90^\circ$ or 1bend $> 120^\circ$ 3score). Additionally, the investigators will utilize IVUS as a tool to evaluate predictor factors to obtain in-depth analyses of the lesions.

[figure not shown]

Figure 1: CTO PCI techniques in trial

4. Statistical analysis

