Discrete data are summarized as frequencies and continuous data as mean \pm SD or median and interquartile range. Chi-square test or Fisher exact test analyses were used for comparison of categorical variables. The multivariable analysis to evaluate the independent contribution of clinical, angiographic, and procedural variables to re-occlusion and in-segment restenosis was performed by forward stepwise logistic regression analysis. Cumulative survival analyses were performed using the Kaplan-Meier method, and the difference between curves was assessed by log-rank test. A multivariable analysis by forward stepwise Cox proportional hazards model was performed to evaluate the independent predictors of death, myocardial infarction, and target CTO vessel revascularization. Odds ratios (ORs), hazards ratios (HRs), and their 95% confidence intervals (CIs) were calculated.

All tests were 2-tailed. A p value <0.05 was considered significant. Analyses

were performed using the software package SPSS (version 11.5, SPSS Inc., Chicago, Illinois).

REFERENCE

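### Forward stepwise selection from an open candidate list is likely to report false predictors of restenosis, with 95% intervals that lose their coverage after selection

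*Combined protocol and SAP*

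**What the plan says.** Finding risk factors is a stated aim. The Abstract (Objectives) intends to "further elucidate some ISR related higher risk factors among CTO PCI patients", and Methods 3, item ⑧ says that "the investigators seek to identify the predictors of ISR".

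Methods 4 gives one multivariable method for this. The "independent contribution of clinical, angiographic, and procedural variables" "to re-occlusion and in-segment restenosis was performed by forward stepwise logistic regression analysis". For death, MI and target CTO vessel revascularization, "A multivariable analysis by forward stepwise Cox proportional hazards model was performed". Odds and hazard ratios are reported with ordinary 95% confidence intervals, two-sided, at p<0.05.

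The section names three classes of variable and lists none. It gives no entry or removal threshold, limit on terms, forced-in term, shrinkage, validation or multiplicity rule.

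The only short list in the plan is in Methods 3, item ⑧: "The standard restenosis scores (R-scores) related six factors including" number of stents, stent length, dissection length, calcification, lumen area and angulation. Section 4 does not restrict the regression to these six.

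**The concern.** Forward selection takes whichever candidate has the strongest association in the data, then the next, and then reports the final model as if it had been chosen in advance. With many candidates and few events this has three effects:

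- Chance associations enter.
- True effects enter mainly when they happen to be overestimated.
- The printed intervals take no account of the search.

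The plan would present the survivors as independent predictors. A reader could act on a list in which a sizeable part is noise and the rest is overstated.

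**Working it through.** **1. The plan's own figure.** Methods 1, item ② wants 60 dissection/re-entry patients at a 20-25% share. 60/0.20 = 300, which reproduces the stated size; 60/0.25 = 240. The sample size was not set with predictor modelling in mind.

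**2. Candidates.** Variables defined in Methods 2 and 3:

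- Angiographic, about 15: occlusion duration, J-CTO score, prior failed attempt (as a J-CTO component), ostial site, proximal/distal site, cap morphology, calcification, tortuosity, proximal disease, distal disease, two side-branch codes ("Proximal or distal cap side branch is considered present if occurring" close to the cap), occlusion length, collateral grade, interventional collaterals.
- Procedural, about 9: antegrade or retrograde, dissection/re-entry or wire escalation, number of approaches ("The number and type of approaches (AWE/ADR/RDR/RWE) required to cross the CTO segment are recorded"), wire crossing time, number of stents, stent length, dissection length, lumen area, post-dilation.

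That is 15 + 9 = 24 before any clinical or further IVUS variable. Some overlap, so I use 20, with 25 as a variant. This is an assumption: defined in the Methods does not mean offered to the model.

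**3. Events (assumption).** No restenosis rate is given. At 10-20% of 300, events are 30-60, or 30/20 = 1.5 to 60/20 = 3.0 per candidate. Methods 1, item ④ limits angiography to successful cases without moderate or severe renal insufficiency. With success of 50-95% (Abstract) and an assumed return of 70-100%, events run from 300 × 0.50 × 0.70 × 0.10 = 10.5 to 300 × 0.95 × 1.00 × 0.20 = 57.

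**4. No real predictors, by formula.** For k independent candidates tested at 0.05, P(at least one false) = 1 − 0.95^k:

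- k = 6: 26.5%
- k = 20: 64.2%
- k = 25: 72.3%

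**5. No real predictors, by simulation.** Forward stepwise logistic regression, n = 300, 30-60 events, normally distributed candidates, score-test entry at p<0.05, Wald removal at p>0.10. Both thresholds are assumed; entry equals the plan's alpha.

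| Candidates | Correlation | At least one false predictor |
|---|---|---|
| 20 | 0 | 62-64% |
| 20 | 0.2 | 57-63% |
| 20 | 0.3 | 52-56% |
| 25 | 0 | 73-74% |
| 6 | 0 | 26-27% |

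The result depends mainly on the number of candidates and little on the event count. With 200 patients, 20 events and 20 candidates it is 66%.

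**6. Some real predictors, 20 candidates, n = 300, 30-60 events.**

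| | 4 true, OR 1.40 per SD, correlation 0.2 | 3 true, OR 1.5 per SD, correlation 0 or 0.3 |
|---|---|---|
| False share of selected variables | 26-35% | 27-42% |
| Inflation of selected true effects | median OR 1.59-1.82 | coefficient × 1.2-1.6 |
| Coverage, all selected | 56-67% | 54-70% |
| Coverage, selected true predictors | 88-92% | 90-96% |

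On the log scale, ln 1.59/ln 1.40 = 0.464/0.336 = 1.38 and ln 1.82/ln 1.40 = 0.599/0.336 = 1.78. The false shares in the right column come from mean counts; for 30 events and correlation 0 they are 0.93/(0.93 + 3 × 0.52) = 0.93/2.49 = 37%.

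**7. Where the coverage goes.** In that same setting, selected true predictors are covered 93.8% of the time. If no false selection were covered at all, pooled coverage would be 1.56 × 0.938/2.49 = 58.8%. The simulated value is 60.5%. Nearly all the loss is therefore due to false selections, whose intervals almost always exclude 1.

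**The case against.** The strongest reply has four parts.

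- **Design label.** Methods 1 calls the study exploratory and non-randomised, the objective is modest, and no validated model is promised. This lowers the severity. It does not restore coverage, and section 4 claims independence rather than calling the findings hypothesis-generating.
- **Assumed inputs.** The event count, the 20 candidates and the thresholds are not in the documents. This stands, and every figure above is conditional on them.
- **The null case is extreme.** The Introduction already cites calcification, occlusion length, lesion complexity and diabetes as reported predictors. This also stands. The setting with four real predictors is the fairer guide, and there about two-thirds to three-quarters of selected variables are genuine. A reader might infer that most reported predictors would be noise; the calculations do not show that.
- **Six factors are listed.** They are, but the regression is not confined to them. Selecting from six would still leave a 26.5% chance of a false predictor when none is real.

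Other stronger readings also lack support. A reader might say the intervals are simply too narrow, but selected true predictors keep 88-96% coverage. A reader might expect the stepwise result to build the R-score, but item ⑧ already fixes its factors and points. Nor do the documents show that the Cox endpoints will have fewer events: no rates are given, clinical follow-up runs to 24 months, and section 4 could mean separate events or one composite. Diabetes appears only as background and is not a listed data item.

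**Conclusion.** The concern holds for the predictor objective. Followed as written, the plan has a substantial chance of reporting false independent predictors and of overstating true ones.

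Assuming 30-60 events, 20 candidates, entry at 0.05 and removal at 0.10:

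- If nothing is predictive, about 55-65% of analyses report at least one false predictor. The lowest setting (30 events, correlation 0.3) gives 52%.
- If four predictors are real at an odds ratio of 1.40 per SD, about 26-35% of selections are false, reported odds ratios are about 1.6-1.8, and intervals of selected variables cover the truth about 56-67% of the time.

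The under-coverage comes mainly from false selections and from estimates pushed away from 1, not from narrow intervals. Fewer returning patients would worsen the inflation: at 200 patients and 20 events, with three true predictors at 1.5 per SD, coefficients are inflated about 1.8-fold. The stepwise Cox models raise the same issue, but I have not put a size on it.

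This should be fixed, but it does not invalidate the primary result. A reader might extend it to the comparison of restenosis between techniques; section 4 compares categorical outcomes by chi-square or Fisher test, which involves no selection.

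**What to change.** Replace both stepwise procedures with one fixed model per endpoint.

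1. Before any 13-month film is read, write a ranked short list of predictors. Include dissection/re-entry versus wire escalation, draw on the R-score factors and occlusion length, and add diabetes if it is collected.
2. Enter the R-score factors as measured values where possible. The bins in Methods 3, item ⑧ leave values unassigned, for example between 35 and 36 mm of stent length, and the middle stent-number category is not a valid range.
3. Take terms from the top of the list according to the total event count, with one rule for all endpoints. At about 10 events per term, 30-60 events allow 3-6 terms. If more are kept, use Firth or ridge penalisation.
4. Keep and report every term with its interval, whatever its p value.
5. Give a bootstrap optimism-corrected c-statistic.
6. Label anything outside the list hypothesis-generating, and do not call it independent.

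The cost is SAP wording and modest programming, possibly in software other than SPSS 11.5. No extra patients are needed; diabetes is used only if it is already collected. The price is a shorter and less striking predictor list. Timing matters: once the films have been read, a prespecified list is no longer credible.

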be a direct consequence of subintimal stenting. If the cause of the high incidence of restenosis is, in fact, due to use of the subintimal space, newer CTO techniques, which are based on controlled subintimal dissection and reentry methods, also would be expected to be associated with this adverse outcome²⁵⁻²⁸ Now there are only limited data about procedural success of ADR and RDR and retrograde techniques have been demonstrated and the use of subintimal stenting did not adversely impact outcomes^{34, 35}. While prospective studies with longer follow-up are needed to assess the long-term safety and efficacy of sub-intimal stenting.

The purpose of the study was therefore to examine the longer-term outcomes of patient who underwent successful CTO PCI in our program, compare the effect of ADR/RDR on outcomes with everolimus-eluting stents (EES) and assess predictors of long-term events.

METHODS

1. Trial overview and study population.

① This clinical trial is a prospective, exploratory, nonrandomized, multicenter trial evaluating the frequency of angiographic restenosis and clinical outcomes among patients undergoing CTO PCI in intimal stent group using antegrade or retrograde wire escalation (AWE/RWE) techniques and sub-intimal stent group using contemporary antegrade or retrograde dissection and re-entry (ADR or RDR) with everolimus-eluting stents (XIENCE Coronary Stent).

② According to high patient's volume registry studies in CTO lesions, the patients percentage of ADR or RDR strategy application was just only 20-25%³⁶⁻³⁷. If to get 60 patients for ADR or RDR strategies, the minimum CTO number are 300 patients. So in our registry study, 300 CTO cases, to which PCI will be attempted, are prospectively enrolled from December 1 2018 to December 31 2019 in the CTO registries of ten centers. The study was approved by the institutional review board at each site. For patients with multiple treated CTO, only the first CTO attempted was considered for the analysis.

③ Exclusions included age <18-years-old or >85-years-old, left ventricular ejection

fraction $\leq 30\%$, allergy to medications (antiplatelet drugs, heparin, metal alloys, or contrast agents), a planned surgery within 6 months of PCI or planned thrombolysis, pregnant, a life expectancy of <6 months.

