④ Patients will sign written informed consent for long-term telephone FU before the interventional procedure. The patients will be followed by a clinical visit or by a telephone interview for 30 day, 6 months and 12 months and 24 months post-procedure for assessment of adverse events. All patients with successful CTO PCI and without moderate or severe renal insufficiency will be scheduled for angiographic follow-up at 13 months. Compared with CTA, coronary angiography to evaluate restenosis is appropriate in all patients especially for severe coronary heart diseases patients with atrial fibrillation and ventricular arrhythmia. It could provide accurate information about mild-severe angulation lesion and the stent straits like total stent length. Procedural and outcome data collection will be collected and entered by operators entered into a dedicated database.

⑤ The study will be performed in accordance with the Declaration of FMMU.

2. Study endpoints and definitions

① The primary study endpoint of the protocol is the binary in-stent restenosis of CTO vessels at the scheduled angiographic follow-up at 13 months. The secondary endpoints are: 1) CTO technique and procedure success rate; and 2) in-hospital and 30 days MACE (Cardiac death, acute myocardial infarction, urgent repeat target vessel revascularization with either pericardiocentesis or surgery and stroke and stent thrombosis and stroke); 6 months and 1-year and 2-year MACE including death, MI, and target CTO vessel revascularization and stroke ; and 3) Restenosis scores (R-scores) of related risk factors.

② Coronary CTOs will be defined as angiographic evidence of total occlusions with TIMI (Thrombolysis In Myocardial Infarction) flow grade 0 and estimated durations of at least 3 months. Estimation of the occlusion duration is based on first onset of anginal symptoms, prior history of myocardial infarction in the target vessel territory, or comparison with a prior angiogram.

③ Procedural success will be defined as angiographic success (final residual stenosis $<30\%$ by visual estimation and TIMI flow grade 3 after CTO recanalization).

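### No technique effect with a 95% CI is prespecified for 13-month restenosis, and the stepwise model is likely to omit it when the result is not significant

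*Combined protocol and SAP*

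**What the plan says.** Methods 2, item 1 sets the endpoint: "The primary study endpoint of the protocol is the binary in-stent restenosis of CTO vessels at the scheduled angiographic follow-up at 13 months". The last paragraph of the Introduction gives comparing the effect of ADR/RDR on outcomes as one purpose of the study, and Methods 1, item 1 describes the study as exploratory and non-randomised.

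Methods 4 (Statistical analysis) contains all the analysis text that bears on this comparison:

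- Discrete data are to be summarised as frequencies.
- For group comparisons: "Chi-square test or Fisher exact test analyses were used for comparison of categorical variables".
- For the multivariable analysis, the sentence covers re-occlusion and ends: "in-segment restenosis was performed by forward stepwise logistic regression analysis". Technique is not said to be forced in, and no entry threshold is given.
- After the survival and Cox models: "Odds ratios (ORs), hazards ratios (HRs), and their 95% confidence intervals (CIs) were calculated". The sentence is tied to no particular comparison.
- "All tests were 2-tailed", and "A p value <0.05 was considered significant".

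Methods 1, item 2 gives the only basis for the sample size: "If to get 60 patients for ADR or RDR strategies, the minimum CTO number are 300 patients". It states no restenosis rate, detectable difference, power or expected precision.

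**The concern.** The main product of a study that compares two techniques on a binary endpoint should be the size of the difference and its uncertainty. Here the named group comparison is a test. No interval is promised for the ISR proportion in either group, although evaluating that frequency is the first stated objective. None is promised for the difference between groups.

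The OR sentence does not close this gap. Under forward stepwise selection, an adjusted OR for technique exists only if technique is selected. Whether it is reported therefore depends on the result, and it is most likely to be missing when the comparison is null. With a subintimal group of about 60, a null result could go with a wide range of true effects, and only an interval would show that.

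The null case is not remote. The Introduction raises the worry that subintimal stenting itself causes restenosis, cites limited earlier data that "the use of subintimal stenting did not adversely impact outcomes", and calls for longer prospective studies of safety and efficacy.

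**Working it through.** **Inputs from the documents.** Two-sided alpha 0.05 (Methods 4); 300 patients, a target of 60 ADR/RDR patients and a 20–25% ADR/RDR share (Methods 1, item 2).

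**Assumptions.** The documents give no ISR rate by technique, so I take control rates of 5% to 20%. A doubling is my illustrative effect. The fold-increase in the Introduction compares CTO with non-occlusive lesions, not the two techniques.

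**The plan's own figure.** 60 / 0.20 = 300, which reproduces it. At a 25% share, 60 / 0.25 = 240, so the plan used the lower share. The range for 300 patients is 300 × 0.20 = 60 to 300 × 0.25 = 75 ADR/RDR patients. This is a feasibility count, and there is no power figure to reproduce.

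**Power for a doubling, 10% v 20%, 60 v 240 (normal approximation).**

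- Pooled rate: (24 + 12)/300 = 0.12.
- SE under no difference: √[0.12 × 0.88 × (1/60 + 1/240)] = 0.0469.
- SE under the alternative: √[0.10 × 0.90/240 + 0.20 × 0.80/60] = 0.0552.
- z = (0.10 − 1.96 × 0.0469)/0.0552 = 0.146, so power is about 0.56.

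Exact enumeration, counting only significant results in the direction of harm, gives power (%) as follows:

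| ADR/RDR v control | Test | 5% v 10% | 10% v 20% | 15% v 30% | 20% v 40% |
|---|---|---|---|---|---|
| 60 v 240 | chi-square | 33.2 | 55.0 | 74.1 | 87.9 |
| 60 v 240 | Fisher | 26.9 | 49.4 | 71.2 | 85.9 |
| 75 v 225 | chi-square | 36.5 | 61.0 | 79.9 | 92.1 |
| 48 v 192 | chi-square | 28.1 | 47.3 | 65.2 | 80.4 |
| 42 v 168 | chi-square | 25.2 | 44.2 | 61.6 | 75.7 |

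The last two rows assume that 80% and 70% of patients have a follow-up film. The documents give no such rate. Some loss is built in, because Methods 1, item 4 schedules angiography only after successful PCI and without moderate or severe renal insufficiency.

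**What a null p value would leave open (illustrative counts, 60 v 240).**

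- *Equal rates, 6/60 v 24/240.* SE of log RR = √(1/6 − 1/60 + 1/24 − 1/240) = 0.433. RR = 1.00, 95% CI exp(±1.96 × 0.433) = 0.43 to 2.34. The risk difference is 0 ± 1.96 × √[0.10 × 0.90 × (1/60 + 1/240)] = ±8.5 percentage points.
- *11/60 v 24/240.* Chi-square p = 0.072 and Fisher p = 0.11. RR 1.83 (0.95 to 3.53), OR 2.02 (0.93 to 4.40), risk difference 8.3 points (−2.2 to 18.8).

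In the second case the analysis as written would show two frequencies and a non-significant p value. The interval, which runs from slight benefit to more than a tripling, is not promised.

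**The case against.** The strongest reply is that the plan already supplies more than a test. Frequencies will be reported, so the crude difference can be read off whatever the p value. The OR sentence carries no condition and does not rule out an unadjusted OR for technique. The study calls itself exploratory, so the lack of a power calculation or margin is not in itself a fault. All of this stands. What remains is that no interval for the technique comparison is guaranteed, and the exploratory label makes estimation with intervals more important, not less.

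Some stronger readings that a reader might infer are not supported:

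- *That the comparison yields only a p value.* The commitment to frequencies contradicts this; what is missing is the interval.
- *That a technique effect with an interval appears only if p<0.05.* The stepwise entry threshold is not stated, and the 0.05 sentence is a general significance rule.
- *That a non-significant result will be reported as no harm.* No section says so. The Introduction's wording about no adverse impact summarises earlier studies, and the next sentence asks for more evidence.

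A further objection concerns the remedy. Methods 3, item 5 makes wire escalation the first choice in all patients, with other strategies after failure. The ADR/RDR group will therefore tend to have harder lesions. A crude risk difference is needed as description, but it cannot alone show that ADR/RDR is not worse. This objection is right, and the fix takes it into account.

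**Conclusion.** The point holds in a limited form. The plan prespecifies no technique effect with a 95% CI for 13-month ISR. It does not force technique into the adjusted model, and it states no expected precision.

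The size of the problem depends on the unknown control ISR rate. At 60 v 240, chi-square power for a doubling runs from about 33% at a 5% control rate to about 88% at 20%. A reader might infer that a doubling is missed about half the time. That is true near a 10% control rate, but the documents give no such rate, and at 15% the miss rate is about 26% (100 − 74). Seventy-five ADR/RDR patients would raise the power figures somewhat, and missing films would lower them.

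One conclusion about a null result needs only an illustrative rate: with 10% observed in both groups, the RR interval of 0.43 to 2.34 still includes a doubling. The plan should be changed, but this does not invalidate the study.

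**What to change.** Amend Methods 4 as follows.

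1. Report, whatever the p value, the ISR proportion in each group with its 95% CI, and the unadjusted risk difference and risk ratio (ADR/RDR against wire escalation) with 95% CIs.
2. Force technique into the multivariable logistic model for restenosis, together with lesion-complexity variables already collected (for example the J-CTO score in Methods 2, item 5), and report its adjusted OR with 95% CI. Keep that set small: at 10% ISR in both groups there would be only about 30 events (300 × 0.10). Stepwise selection can remain for the separate search for predictors.
3. State that p≥0.05 will not be reported as no difference or no adverse impact, and that any such statement will refer to the upper limit of the adjusted interval.
4. State the precision expected with 60 to 75 ADR/RDR patients, and with fewer if films are missing.

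A margin fixed by the sponsor before the films are read is optional in an exploratory registry. If one were set on the unadjusted risk difference, the ±8.5 points above shows that a margin smaller than that could not be met with 60 v 240 even at equal observed rates of 10%.

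The cost is wording and a few extra lines of output, with no added patients or data. The downside is that a null result will read less favourably, because its interval will be wide.
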